7.1 Sample Size Determination

Twenty eight patients will be recruited into each arm, for a total of 84 patients. This number has been chosen for feasibility rather than based on a formal power analysis. We will use this study to provide data for a formal power analysis in order to power a larger study.

7.2 Statistical Methods

Descriptive and Inferential Statistics

Continuous variables will be summarized with the sample mean, median, standard deviation, minimum, 25th percentile, 75th percentile, and maximum. Categorical variables will be summarized with number and percentage of patients. All analysis will be performed on the basis of the intention-to-treat principle. Comparisons of endpoints between the three treatment arms will be made using a Wilcoxon rank sum test (continuous or ordinal endpoints) or Fisher's exact test (categorical endpoints). Missing data will be imputed using either the last observation carried forward method, a regression-based approach, or another method, depending on the extent of missing data. In order to adjust for the three pair-wise comparisons between treatment groups that will be made for each endpoint, we will utilize a Bonferroni correction for multiple testing, after which p-values of < 0.0167 will be considered as statistically significant. All statistical tests will be two-sided.

Primary Hypothesis:

We hypothesize that the intermittent bolus infusion cohort will report improved pain scores compared to continuous infusion catheters and placebo cohorts.

Secondary Hypothesis:

We hypothesize that the intermittent bolus cohort will require fewer doses of patient-administered medication and will use narcotic medication for a shorter duration when compared to the continuous infusion and placebo groups.

Interim Analysis

We will evaluate the first twenty patients. If 50% of the patients are withdrawn from the study for poor pain control or serious adverse reactions to the study medication, then we will close the study early.

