7.3	Subject Population(s) for Analysis	19
8	Safety and Adverse Events	19
8.1	Definitions	19
8.2	Recording of Adverse Events	20
8.3	Reporting of Serious Adverse Events and Unanticipated Problems	21
8.3.1	Sponsor-Investigator reporting: notifying the Mayo IRB	21
8.3.2	Sponsor-Investigator reporting: Notifying the FDA	21
8.4	Unmasking/Unblinding Procedures	21
8.5	Stopping Rules	21
8.6	Medical Monitoring	21
8.6.1	Internal Data and Safety Monitoring Board	22
9	Data Handling and Record Keeping	23
9.1	Confidentiality	23
9.2	Source Documents	23
9.3	Case Report Forms	23
9.4	Records Retention	24
10	Study Monitoring, Auditing, and Inspecting	24
10.1	Study Monitoring Plan	24
10.2	Auditing and Inspecting	25
11	Ethical Considerations	25
12	Study Finances	25
12.1	Funding Source	25
12.2	Conflict of Interest	25
13	Publication Plan	25

14 References

25

List of Abbreviations**LIST OF ABBREVIATIONS**

AE	Adverse Event/Adverse Experience
CFR	Code of Federal Regulations
CRF	Case Report Form
DSMB	Data and Safety Monitoring Board
FDA	Food and Drug Administration
GCP	Good Clinical Practice
HIPAA	Health Insurance Portability and Accountability Act
IB	Investigator's Brochure
IND	Investigational New Drug Application
IRB	Institutional Review Board
PHI	Protected Health Information
PI	Principal Investigator
SAE	Serious Adverse Event/Serious Adverse Experience
SOP	Standard Operating Procedure
TKA	Total Knee Arthroplasty
OME	Oral Morphine Equivalents

Study Summary

Title	A Three-Arm, Double-Blinded, Randomized Controlled Trial Comparing the Efficacy of Adductor Canal Pain Catheters following Total Knee Arthroplasty
Running Title	Adductor Catheter Efficacy Following Total Knee Arthroplasty
Protocol Number	Pending
Phase	Phase III
Methodology	Double-Blinded Randomized Controlled Trial
Overall Study Duration	12 months
Subject Participation Duration	60 days, or until discontinuation of narcotic medication (whichever is later)
Single or Multi-Site	Single Center
Objectives	
 • Aim 1 will be to compare postoperative pain levels between groups • Aim 2 will be to compare use of the patient-administered dosing between groups • Aim 3 will be to compare duration of narcotic use between groups
Number of Subjects	84
Diagnosis and Main Inclusion Criteria	Narcotic naïve patients who have a diagnosis of osteoarthritis and are undergoing a primary total knee arthroplasty are eligible for the study.

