We previously reported on risk factors for patients requiring additional opioid prescriptions following surgery and have demonstrated that a collaborative approach between the anesthesia and orthopedic teams, utilizing both local and regional nerve blocks, reduced pain scores with a simultaneous 43% decrease in oral morphine equivalents consumed during the hospitalization.^{10,11} Additional studies have focused on multimodal pain regimens, but have not evaluated the efficacy of these regimens with adductor pain catheters.¹²⁻¹⁷ We recently performed a randomized, prospective, double-blinded, placebo-controlled trial using a multimodal regimen with and without schedule II opioids following total knee arthroplasty. In that study we utilized an adductor canal pain catheter with a continuous infusion for four days postoperatively. We demonstrated equivalent postoperative pain scores in the oxycodone and placebo group with use of the adductor catheter. However, despite these similar pain scores, 20% of the oxycodone cohort required continued narcotic medication at 60 days postoperatively (*submitted for publication*).

It is currently unknown if a continuous infusion is the most efficacious form of medication delivery through the catheter. Recent studies have begun to evaluate intermittent bolus infusions, with the belief that catheter placement is less critical when compared to a continuous infusion.

Our study is intended to directly compare these delivery modes in a double-blinded, randomized controlled trial.

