3.5 Secondary Study Endpoints

The secondary endpoints will be the amount of medication administered via the patient-controlled function on the adductor catheter as well as duration of narcotic use required in each cohort. We hypothesize that the intermittent bolus cohort will require fewer doses of patient-administered medication and will use narcotic medication for a shorter duration when compared to the continuous infusion and placebo groups.

We will additionally calculate the overall morphine equivalents used in each cohort during their hospitalization, and dividing this by the total number of post-surgical hospitalization hours in order to normalize the data.

Nausea and vomiting will be recorded daily using the postoperative nausea and vomiting scale and compared between groups. Presence of constipation will be a subjective rating by the patient that is also recorded daily. We will compare the post-surgery length of hospitalization between groups. Finally, we will compare patient-reported outcomes using the KOOS Jr. questionnaire.

We hypothesize that the intermittent bolus cohort will use less narcotic mediation and will therefore have lower rates of constipation, nausea and vomiting. Furthermore, we believe this cohort will demonstrate equivalent lengths of stay and patient-reported outcomes as compared to the comparison groups.

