8.5 Stopping Rules

Subjects will be withdrawn from the study if they have a serious adverse reaction to any of the study drugs. Additionally, if patients are unable to complete the follow-up questionnaires they will be withdrawn. If patient's pain increases during the study period that is not tolerable without additional narcotic medication they will be withdrawn. Finally, we will withdraw patients from the study that no longer wish to participate.

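### Duration of narcotic use (Aim 3) has only a rank sum test and no censoring rule, and the plan conflicts on how a withdrawn patient's duration is handled

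*Combined protocol and SAP*

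**What the plan says.** The Study Summary states that "Aim 3 will be to compare duration of narcotic use between groups". Section 3.5 makes this a secondary endpoint, with the hypothesis that the bolus arm "will use narcotic medication for a shorter duration when compared to the continuous infusion and placebo groups". Section 7.2 repeats the hypothesis.

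For the analysis, Section 7.2 states: "Comparisons of endpoints between the three treatment arms will be made using a Wilcoxon rank sum test (continuous or ordinal endpoints"). Significance is judged pairwise, "after which p-values of < 0.0167 will be considered as statistically significant", and "All statistical tests will be two-sided". The documents name no time-to-event method, do not define the event and give no censoring rule.

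The handling of patients who leave early is spread over five places:

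- **Section 3 (Study Design):** directly after the early-withdrawal rule, it says weekly questionnaires go on establishing narcotic duration until the patient has stopped.
- **Section 4.4.2:** for withdrawn subjects, data from before withdrawal are collected.
- **Section 7.2:** analysis is by intention to treat. Missing data are imputed by last observation carried forward, regression or some other method, chosen according to how much is missing.
- **Section 7.3:** the final analysis includes patients who completed the study.
- **Section 8.5:** "if patients are unable to complete the follow-up questionnaires they will be withdrawn". Patients whose pain becomes intolerable without more narcotic are withdrawn too.

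**The concern.** A patient last known to be using narcotics on day 10 has a duration of at least 10 days, not of 10 days. A rank sum test has no place for that information. The patient must be dropped, given an imputed value, or ranked as if use had ended on day 10, and the plan does not say which.

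Such patients are foreseeable. Section 8.5 ties withdrawal to non-response and to pain that needs more narcotic, and one arm receives saline through the catheter, so loss could differ by arm and depend on the outcome. Long durations are also expected: in the sponsor's earlier trial "20% of the oxycodone cohort required continued narcotic medication at 60 days postoperatively".

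If cut-off values were ranked as complete, an arm losing more patients would seem to stop narcotics sooner than it did. Section 7.1 also intends these data to power a larger study, so a distorted duration estimate would carry into that design.

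**Working it through.** **Figures in the plan.** Three pairwise comparisons give 0.05/3 = 0.01667, which rounds to the stated 0.0167. "Twenty eight patients will be recruited into each arm, for a total of 84 patients": 3 × 28 = 84. No power is stated, so there is none to reproduce.

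**The handling rules side by side.** For a patient withdrawn on day 10 while still using:

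| Section | Value entering the test |
|---|---|
| 3 | true duration, found by later questionnaires |
| 4.4.2 | cut off at day 10 |
| 7.2 | imputed; carrying forward the accrued days gives day 10 again |
| 7.3 | excluded, if not counted as having completed |

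Only the first gives a true duration, and it depends on the patient still responding.

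**Simulation, log-normal model.** From the plan: 28 per arm, two-sided threshold 0.05/3. Assumed: median 21 days and about 15% beyond 60 days, so the SD of log duration is ln(60/21)/1.036 ≈ 1.01; loss on days 3–14, unrelated to individual duration; true effect either none or 1.8-fold shorter on bolus. There were 3,000 to 4,000 trials per scenario, and ranges are across repeated runs. In this table the rank sum test uses cut-off values as complete.

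| Loss, placebo v bolus | No effect: rank sum | No effect: log-rank | 1.8-fold: rank sum | 1.8-fold: log-rank |
|---|---|---|---|---|
| none | – | – | 36–37% | 35–36% |
| 20% v 20% | 2.0% | – | 24–25% | 31–34% |
| 10% v 5% | 2.0% | 2.2% | 25% | 33–34% |
| 25% v 5% | 5.5–6.8% | 2.1–2.5% | 9% | 32–33% |

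At 25% v 5% with no effect, nearly all false rejections (6.1 of 6.2 percentage points in one run) made the arm with more loss look faster to stop. In another run only 0.03% favoured bolus.

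A rank sum test on completers only, at 25% v 5%, had type I error of 1.8–2.0% and power of 23–29%. The lower power figures arise when only patients with cut-off durations are dropped, the higher when everyone lost is dropped.

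**Second model, as a check on shape.** Exponential durations with 20% still using at day 60, so the rate is −ln(0.2)/60 = 0.0268 per day; loss on days 1–14; alternative hazard ratio for stopping of 2; 4,000 trials per scenario.

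| Scenario | Type I: rank sum / log-rank | Power: rank sum / log-rank |
|---|---|---|
| no loss | 0.016 / 0.018 | 0.40 / 0.53 |
| common cut at day 60 | 0.012 / 0.017 | 0.40 / 0.50 |
| 20% both arms | 0.015 / 0.023 | 0.23 / 0.46 |
| 5% v 20% | 0.048 / 0.022 | 0.12 / 0.50 |
| 5% v 30% | 0.100 / 0.016 | 0.05 / 0.47 |

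The log-rank advantage with no loss (0.53 v 0.40) comes from the proportional hazards built into this model, not from censoring.

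When longer users were made more likely to leave, at 5% v 30%, type I error was 0.218 for the rank sum test on cut-off values, 0.048 on completers only and 0.033 for log-rank. No test is fully protected when leaving depends on the outcome.

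**The case against.** A reader might infer that the plan treats cut-off durations as complete and so distorts the error rate for Aim 3. The documents do not support that. No section says cut-off values are ranked as complete. Section 3 intends duration to be followed until narcotics stop, and the Study Summary sets participation at 60 days or until narcotics stop, whichever comes later. Staff contact patients who miss a questionnaire (Sections 3 and 6.3), and Section 3.7 asks for the date of last use, so a later contact can recover a duration. If all this works, every duration is complete and the rank sum test is valid.

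A general claim of inflated type I error does not stand either. With equal loss unrelated to duration, or a common day-60 cut, there is no material inflation. Where loss is heavier on placebo, the excess runs against bolus, so false support for the trial's hypothesis becomes rarer.

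Nor does the 12-month overall duration show that long-term users will be cut off, because no data cut-off is stated.

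Finally, this is a secondary endpoint in a pilot sized for feasibility with no power claimed, so no stated figure becomes wrong.

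What remains is the conflict with Sections 4.4.2 and 7.3, and the fact that Section 3 cannot supply a stop date for someone who no longer answers. Pilot status does not remove the issue, because Section 7.2 plans formal tests of this endpoint.

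**Conclusion.** The point holds in a conditional form. Section 7.2 offers no way to represent a patient still using narcotics at last contact, and Sections 3, 4.4.2, 7.2 and 7.3 must be reconciled on what enters the analysis.

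The size depends on which handling is chosen:

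- **Complete follow-up:** no defect in the test.
- **Cut-off values used as complete:** power falls even with equal or modest loss, to about 25% v 33–34% for log-rank in the log-normal model, and to 9% v 32% at 25% v 5%. Type I error reaches about 6–7% at 25% v 5% but stays near 2% with equal loss or 10% v 5%. The excess works against the arm losing fewer patients.
- **Completers only:** type I error holds if loss is unrelated to duration, but power is lower (from 23%, v 32%, at 25% v 5%). The comparison can be biased if withdrawal depends on pain, as Section 8.5 makes possible.

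Loss rates, distribution shapes and effect sizes are assumptions; the documents give none except the 20% at day 60. The plan should be changed before the data are unblinded for analysis.

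**What to change.** In Section 7.2, give narcotic duration its own paragraph:

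1. **Event and origin.** Time from surgery to the date of last use, taken from the Section 3.7 question once the patient confirms having stopped. A last reported use date alone is not enough, since it also exists for patients lost while still using. State a rule for resumed use, because Sections 3.1 and 5.6 allow further prescriptions.
2. **Censoring.** Censor patients still using at last contact on that date, with no carry-forward for this endpoint.
3. **Analysis.** Kaplan-Meier curves and pairwise log-rank tests at 0.0167 in all randomised patients, with the Kaplan-Meier proportion still using at days 30 and 60 and confidence intervals.
4. **Sensitivity.** Repeat the analysis treating patients withdrawn for pain as continuing users.
5. **Reconciliation.** Align Section 4.4.2 with Section 3 on whether duration is still collected after withdrawal, and Section 7.3 with the intention-to-treat statement. The clinical withdrawal rules are not at issue here.

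The cost is mainly wording, plus questionnaire follow-up that Section 3 already appears to intend. In the log-normal model with no loss, log-rank gave 35–36% power against 36–37% for the rank sum test. The downside is that log-rank still assumes remaining censoring is unrelated to narcotic use, so whether duration is collected after withdrawal matters as much as the choice of test.

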3.7 Identification of Source Data

The following source data will be directly recorded on the Case Report Form (CRF) at the pre-op visit and inputted into REDcap, a password protected database.

- Name
- Medical Record Number
- Email address
- Date of Birth, Age
- Gender
- Race
- Weight (lbs), Height (In), BMI
- Previous surgeries? (yes, no)
- Are you taking Nsaids? (yes, no)
- Previous injections (yes, no)
- Baseline NRS score
- Laterality of surgery
- KOOS Jr. Questionnaire
- Device serial number

The following source data will be recorded daily for two weeks using an online questionnaire recorded into REDcap, and continued weekly until discontinuation of narcotic medication. This data will again be collected at 30 and 60 days following the date of surgery.

- Name
- Medical Record Number
- Date of Birth
- How long has it been since your operation? (Less than 1 month, 1-2 months, Greater than 2 months)
- Are you using narcotic medication? (yes/no)
 - What was the date you last consumed narcotic medication? (if no to previous answer)
- How would you rate the pain you have been experiencing? (0-10)

- Have you been experiencing constipation over the past 24 hours? (yes, no)
- Have you been vomiting or had dry-retching over the past 24 hours? (once, twice, three or more times, no)
- Have you been experiencing a feeling of nausea (an unsettled feeling in the stomach and slight urge to vomit) over the past 24 hours? (yes, no)
- KOOS Jr. Questionnaire (only recorded during 1 month and 2 month questionnaires)
- Rate of on-demand catheter use (recorded at final survey only)

4 Subject Selection Enrollment and Withdrawal

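### Section 7.2 leaves the imputation method open and carries no imputation uncertainty into the tests, and some of the choices it permits do not hold the 0.0167 level

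*Combined protocol and SAP*

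**What the plan says.** Section 7.2 covers missing data in one sentence: "Missing data will be imputed using either the last observation carried forward method, a regression-based approach, or another method". The choice among these is to be made "depending on the extent of missing data", and no cut-off is given for it. The section does not say whether imputation is single or multiple, what the regression contains, or whether arm is a predictor. It names no combining rule and no sensitivity analysis.

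Comparisons "will be made using a Wilcoxon rank sum test (continuous or ordinal endpoints) or Fisher's exact test (categorical endpoints"). The only error control is a Bonferroni correction, introduced "In order to adjust for the three pair-wise comparisons between treatment groups that will be made for each endpoint", "after which p-values of < 0.0167 will be considered as statistically significant". The plan adds: "All statistical tests will be two-sided".

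Other sections bear on the point:
- Section 3 (Study Design) fixes carry-forward of the last pain score to study end for withdrawn patients.
- Section 7.3 bases the final analysis on patients who completed the study, whereas 7.2 calls for intention to treat.
- Section 8.5 withdraws patients whose pain is not tolerable without additional narcotic, and patients unable to complete the questionnaires.
- Section 3.7 lists "Rate of on-demand catheter use (recorded at final survey only"), so demand use has one reading per patient.

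**The concern.** A rank sum or Fisher test takes one completed data set and counts every value in it as a full observation. If a missing value is filled in once and nothing further is done, the p-value takes no account of the guess.

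This matters most when the fill-in uses arm. Imputed values then sit on that arm's own fitted line, so a chance deviation in the arm is repeated in its imputed values and the within-arm spread shrinks, while n stays at 28. If arm is left out, the imputed values carry almost no treatment difference and the comparison is pulled toward zero.

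Demand use is a named secondary endpoint with no earlier value to carry forward. Of the two methods that 7.2 names, only regression can fill it. The wording also allows the method to be picked after the data are seen, which adds a route to false positives. At stake are the significance claims at 0.0167 and, because Section 7.1 says the data will be used to power a larger study, the standard deviations passed to that study.

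**Working it through.** **Inputs from the plan.** Three arms of 28 (3 × 28 = 84, Section 7.1); three pairwise two-sided tests per endpoint at 0.0167 (Section 7.2). The plan states no expected dropout, standard deviation or effect size, so those below are assumptions.

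**The plan's own figure.** 0.05 / 3 = 0.01667, which rounds to 0.0167. It reproduces.

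**Null simulations (no true difference).** The familywise error is the chance of at least one p<0.0167 among the three pairs.
- *Simulation 1*: values missing at random, baseline-outcome correlation 0.4, predicted-value regression on baseline with or without arm, 4,000 replicates.
- *Simulation 2*: 14 daily scores with mean falling from 5.5 to 3, between- and within-patient SD 1.5 each, pain-related dropout in week 1, 20,000 replicates.

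The Monte Carlo standard error is √(p(1−p)/R): at p = 0.23, R = 4,000 it is 0.007; at p = 0.19, R = 20,000 it is 0.003. With nothing missing, the familywise error is 0.041 (simulation 1) and 0.039 (simulation 2, final-day score).

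Equal missingness in all arms:

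| Method | 10% | 20% | 30% |
|---|---|---|---|
| Regression with arm, simulation 1 | 0.079-0.080 | 0.133-0.141 | 0.227-0.230 |
| Regression within arm, simulation 2 | 0.071 | 0.125 | 0.191 |
| Same, with a random residual added | 0.062 | 0.091 | 0.131 |
| Carry-forward, final day | 0.038 | 0.042 | 0.040 |
| Regression pooled over arms, simulation 2 | 0.039 | 0.040 | 0.042 |
| Smaller p of carry-forward and pooled regression | 0.051 | 0.061 | 0.065 |

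A further run with arm in the model gave about 0.07, 0.15 and 0.22. Without arm, simulation 1 gave 0.040-0.043 and the further run 0.039-0.044.

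Unequal dropout (simulation 2, percent per arm):

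| Method | 10/10/30 | 5/20/40 | 10/10/50 |
|---|---|---|---|
| Carry-forward, final day | 0.057 | 0.081 | 0.109 |
| Carry-forward, 14-day mean | 0.044 | 0.049 | 0.053 |
| Regression pooled over arms | 0.041 | 0.045 | 0.043 |

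Under carry-forward the mechanism is bias: scores fall over time, so the arm with more early dropout keeps more high early scores.

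**14-day mean NRS.** A daily-score version of simulation 1 (intraclass correlation 0.5, 1,500 replicates) gave 0.041, 0.049, 0.065 and 0.063 at 0, 10, 20 and 30% dropout.

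**Fisher tests** (event rate 20% or 40%). The familywise error is 0.018-0.024 with nothing missing and at most 0.041 under carry-forward. A single within-arm draw gives 0.061-0.122 at 20-30% equal dropout.

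**Cost of leaving arm out.** With 20% missing in both arms and imputed values carrying no arm difference, the expected difference is (1 − 0.20)δ = 0.80δ. The simulated ratio was 0.79, a 21% shrinkage. Power at 0.9 SD was 0.596, against 0.644 from observed values alone (2,000 replicates).

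**Effect on the SD.** With correlation 0.4, no true difference and a fraction m replaced by predicted values, the completed-data variance is (1 − m) + 0.4²m times the true variance: 0.916, 0.832 and 0.748 at m = 0.1, 0.2 and 0.3. Required sample size scales with variance, so a later trial planned from that SD would be about 8%, 17% or 25% too small.

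**The case against.** The strongest reply is that the plan never commits to the harmful variant. It does not say that the regression is single, that arm is a predictor, or that imputed values are tested as though observed, and its third option could be multiple imputation. That is correct: the defect is an open choice with no uncertainty step, not a stated wrong method.

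A reader might also infer that the 0.0167 threshold fails whenever data are missing and imputed once. The documents and the calculations do not support this. Carry-forward uses only each patient's own data, so with no treatment effect and equal dropout the arms stay exchangeable and the rank test keeps its level. Regression without arm kept the level in every pattern tried.

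Three further replies carry some weight:
- The effect on the 14-day mean is small, and Section 3 has staff contact patients who miss a questionnaire, which limits intermittent gaps.
- Demand use is read from the returned pump rather than from a survey answer, and daily pain scores from the same days could inform its imputation.
- The trial is a pilot sized for feasibility.

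These lower the severity. They do not remove the point, since the plan still declares significance at 0.0167. The completer population in 7.3 would leave little to impute, but it contradicts the intention-to-treat statement in 7.2, so it cannot serve as a defence. Equal dropout cannot be taken for granted either: one arm's pump holds saline, and intolerable pain leads to withdrawal.

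**Conclusion.** The point holds as one of open specification. Section 7.2 permits several methods, lets the extent of missing data decide among them, and has no step that brings imputation uncertainty into the test.

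Some permitted choices do not hold the level. Single regression with arm in the model gives a familywise error of about 7-8%, 13-15% and 19-23% at 10, 20 and 30% missing. Carry-forward to a late score gives about 6-11% when dropout is unequal. Other choices do hold it, but arm-blind single imputation shrinks true differences. For the 14-day mean NRS the rise is modest, from about 4% to 6.5%.

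The sizes rest on assumed missing-data rates, correlations and pain trajectories. The inflation with arm in the model appeared under two different sets of assumptions and in a further run. Because this is a pilot, the point is a change that should be made rather than a fatal fault.

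**What to change.** Replace the open list in 7.2 with one method per endpoint that applies whatever the extent of missing data, and amend the carry-forward sentence in Section 3 to match. Suggested content:

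- Endpoints with missing values: multiple imputation (for example 50 sets) with arm, baseline and all observed daily scores in the model.
- Pool between-group estimates and their standard errors by Rubin's rules. These rules do not apply directly to rank sum or Fisher statistics. For rank-based comparisons, pool the Mann-Whitney probability with its variance, which keeps the planned Wilcoxon-type comparison. For binary endpoints, pool a risk difference or log odds ratio.
- For repeated NRS scores, a likelihood-based mixed model using all observed scores is an acceptable alternative.
- Add a sensitivity analysis for pain-related withdrawal. The methods above assume data missing at random, and multiple imputation alone does not necessarily cure bias from withdrawals driven by pain.
- Reconcile the intention-to-treat statement in 7.2 with the completer population in 7.3.

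The level under the replacement was not simulated here; the same null set-up can check it before the plan is final. The cost is SAP and protocol wording, some programming, and somewhat larger p-values when data are missing. No new patients or data are needed.

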3.4 Primary Study Endpoints

The primary endpoint will be pain scores, calculated by the Numerical Rating Scale. This score will be collected daily during the hospital examination and by online or phone surveys after discharge. We will calculate the mean difference in recorded pain scores between cohorts. We hypothesize that the intermittent bolus infusion cohort will report improved pain scores compared to continuous infusion catheters.

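### Section 7.2 holds all three pairwise tests at 0.0167; a step-down rule would keep every rejection, add some, and stay within 5% familywise error per endpoint (optional improvement, not an error)

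*Combined protocol and SAP*

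**What the plan says.** Section 7.2 compares the arms by Wilcoxon rank sum tests for continuous or ordinal endpoints and Fisher's exact tests for categorical ones, and adds "All statistical tests will be two-sided". The multiplicity family is defined per endpoint: "In order to adjust for the three pair-wise comparisons between treatment groups that will be made for each endpoint". The rule is then "we will utilize a Bonferroni correction for multiple testing, after which p-values of < 0.0167 will be considered as statistically significant". No ordering, step-down rule, global gate or covariate is named.

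The primary hypothesis in section 7.2 is "We hypothesize that the intermittent bolus infusion cohort will report improved pain scores compared to continuous infusion catheters and placebo cohorts". Section 3.4 states it against continuous infusion only. Section 3.4 also promises an estimate: "We will calculate the mean difference in recorded pain scores between cohorts". No interval is planned for it.

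On the 28 patients per arm, section 7.1 says "This number has been chosen for feasibility rather than based on a formal power analysis". Section 3.7 lists "Baseline NRS score" among the pre-operative data.

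**The concern.** Because the sample size is fixed by feasibility, any extra efficiency has to come from the analysis. The plan still declares significance for every endpoint, and its section 7.2 hypothesis needs two rejections: bolus versus continuous and bolus versus placebo. Holding the second and third tests at 0.0167 after the first has succeeded gives up rejections that the 5% familywise level implied by 0.05/3 would allow. Likewise, a baseline measure of the primary outcome is collected and no analytic use is specified, although it could narrow the interval around the promised mean difference.

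**Working it through.** **The plan's figure.** 0.05/3 = 0.01667, which rounds to 0.0167 (3 × 0.0167 = 0.0501, rounding only). The threshold reproduces.

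**Why step-down is valid.** The three nulls are equality of bolus and continuous, bolus and placebo, and continuous and placebo. Two of them being true forces the third, so the number of true nulls is 0, 1 or 3.
- All three true: an error needs the smallest p-value to be below 0.05/3, which has probability at most 3 × 0.05/3 = 0.05.
- Exactly one true: an error needs that pair's p-value to be below 0.05, which has probability at most 0.05.

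So the thresholds 0.0167, then 0.05 and 0.05 (Shaffer) control familywise error at 5%. Holm uses 0.0167, 0.025, 0.05. Both keep 0.0167 for the first step and relax only later ones, so no Bonferroni rejection can be lost.

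**Size of the gain.** Inputs from the documents: 28 per arm, two-sided Wilcoxon tests, three pairs. The documents give no effect size or SD, so the effects are assumptions. Simulation: 40,000 trials per scenario, normal data, normal-approximation rank sum test. Means are bolus/continuous/placebo in SD units; lower is less pain. Entries are Bonferroni → Holm → Shaffer.

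| Assumed means | Bolus vs continuous | Both bolus contrasts | Any rejection (all rules) |
|---|---|---|---|
| −1.0/−0.5/0 | 26 → 35 → 42% | 25 → 34 → 42% | 89% |
| −0.75/0/0 | 60 → 64 → 68% | 44 → 51 → 61% | 76% |
| −0.3/0/0 | 9 → 10 → 11% | 3 → 4 → 6% | 16% |

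No simulated Bonferroni rejection was lost. For winning both contrasts, Shaffer at 28 per arm matches Bonferroni at about 42 to 43 per arm in the first scenario and 36 in the second. With rounded 0–10 scores (latent SD 2.3, also assumed), the chance of winning both goes from 28% to 43% at observed means 1.9/3.1/3.1, from 16% to 29% at 1.5/2.2/3.1, and from 3% to 6% at 2.5/3.1/3.1.

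**Size of the price.** With all arms equal, familywise error is the same under all three rules (about 4%). With one truly equal pair, the error for that pair goes from Bonferroni to Shaffer as follows:
- Continuous versus placebo: 1.4 → 2.7% at −0.3/0/0; 1.6 → 4.7% at −0.75/0/0; 1.6 → 5.0% at −1.5/0/0.
- Bolus versus continuous, when both active arms beat saline: 1.6 → 4.8% at −0.75/−0.75/0.

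The largest familywise error in any scenario was 5.1%, with a Monte Carlo standard error of √(0.05 × 0.95/40,000) = 0.11 points, so it is consistent with the 5% bound.

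**Baseline adjustment.** The 95% CI half-width in SD units is t(0.975, 53 df) × √[(2/28)(1 − r²)], with t = 2.006 and √(2/28) = 0.267. The detectable difference is for 80% power at alpha 0.0167 (noncentral t, 54 df unadjusted, 53 adjusted). The correlation r is not in the documents.

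| Assumed r | CI half-width | Detectable difference |
|---|---|---|
| 0 (unadjusted) | 0.54 | 0.89 |
| 0.2 | 0.53 | 0.87 |
| 0.3 | 0.51 | 0.85 |
| 0.5 | 0.46 | 0.77 |

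**The case against.** The best defence is that nothing here is wrong. Bonferroni is valid and simple, and it has matching 98.33% intervals, which suits what section 3.2 calls a pilot. The large gains need assumed effects of 0.5 SD or more between bolus and continuous; at 0.3 SD they are a few points. This stands, and it is why the point is optional. It does not remove the point, because section 7.2 still declares significance on each endpoint and the change costs one sentence.

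A second objection is that step-down may not be the most efficient rule. If section 3.4 governs, the single contrast of bolus versus continuous could be tested alone at 0.05, with about 76% power at −0.75/0/0 against 68% under Shaffer. If only the joint claim against both comparators matters, testing each at 0.05 needs no split and gives about 64% against 61%. This also stands: the two statements of the primary hypothesis should be reconciled first.

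Four stronger readings are tempting, and the documents do not support them.
- *The 0.0167 rule is an error.* It reproduces and controls error within an endpoint.
- *Step-down gains power at the same error.* Familywise error is unchanged only when all arms are equal. Otherwise it rises, within 5%, and this includes false bolus-versus-continuous claims.
- *The primary hypothesis succeeds only if bolus beats both comparators.* That follows section 7.2 but not section 3.4.
- *Baseline NRS goes unused.* The documents only leave its use unspecified: neither the dynamic allocation factors (section 3) nor the covariates of the optional regression imputation (section 7.2) are named.

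**Conclusion.** The point holds as a cheap, optional improvement. Within each endpoint, a step-down rule rejects everything Bonferroni rejects, and sometimes more, at a familywise error of no more than 5%. At 28 per arm the chance of winning both bolus contrasts rises by about 17 percentage points under the two larger assumed effect patterns and by about 3 under the smallest. The chance of a first rejection never changes, and power stays low if effects are small. The validity argument needs no assumed effect size, but takes each null to be equal distributions in the two arms; the size of the gain rests on the assumed effects. Baseline adjustment is a sound secondary step whose value depends on an unknown correlation. Error across endpoints and days is uncontrolled now and would remain so.

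**What to change.** First, reconcile sections 3.4 and 7.2 on which contrasts are primary. If there is a single primary contrast, it can be tested at 0.05 without a split.

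**(1) Main change.** If all three pairs stay in the family, keep the Wilcoxon and Fisher tests and replace the 0.0167 sentence in section 7.2 with:

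> For each endpoint, if the smallest of the three pairwise p-values is < 0.0167, that pair is declared significant and each remaining pair is tested at 0.05; otherwise no pair is declared significant.

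Holm (0.0167, 0.025, 0.05) is the simpler minimum. The change should be made before unblinded data are seen. It costs SAP wording only. The plan should state the downsides: a higher error rate for a remaining true null (up to 5%), no simple matching simultaneous intervals, and no control across endpoints or days.

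**(2) Secondary change.** Once the patient-level NRS summary and time window are fixed, which section 3.4 does not do, report the promised mean difference adjusted for baseline NRS (ANCOVA in the two arms compared, or a rank-based equivalent). Label its 95% CI as unadjusted for multiplicity, and state that the Wilcoxon result decides significance. No new data are needed. Interval and test can disagree: in simulation, at least one CI excluded zero for a non-significant pair in 9% of trials with all arms equal. With effects present this was 16–18% of trials at r = 0 and 26–38% at r = 0.5. The reverse occurred in 1.5–8%.
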